### 14.2 Immunogenicity Analysis

TABLE 14.2.1.1(a):
Secondary Analysis of Percentages of Participants with a ≥4-fold Increase in rSBA Titer on Day 29, by Serogroup
- Per Protocol Population

	Meningococcal Polysaccharide										
Treatment Crown		A		C		Y		W		X	
Treatment Group (Number of Participants)	n (%)	95% CI a	n (%)	95% CI a	n (%)	95% CI a	n (%)	95% CI a	n (%)	95% CI a	
≥ 4-Fold Increase											
Adjuvanted MCV-5 (N=XX)	x (x.x)	xx.x - xx.x	x (x.x)	xx.x - xx.x	x (x.x)	xx.x - xx.x	x (x.x)	xx.x - xx.x	x (x.x)	xx.x - xx.x	
Non-adjuvanted MCV-5 (N=XX)	x (x.x)	xx.x - xx.x	x (x.x)	xx.x - xx.x	x (x.x)	xx.x - xx.x	x (x.x)	xx.x - xx.x	x (x.x)	xx.x - xx.x	
Menactra® (N=XX)	x (x.x)	xx.x - xx.x	x (x.x)	xx.x - xx.x	x (x.x)	xx.x - xx.x	x (x.x)	xx.x - xx.x	x (x.x)	xx.x - xx.x	
Treatment Group Difference	%	95% CI a	%	95% CI a	%	95% CI a	%	95% CI a	%	95% CI a	
Adjuvanted MCV-5 - Non-Adjuvanted MCV-5	XX.X	XX.X-XX.X	XX.X	xx.x-xx.x	XX.X	XX.X-XX.X	XX.X	xx.x-xx.x	XX.X	xx.x-xx.x	
Adjuvanted MCV-5 - Menactra®	XX.X	xx.x-xx.x	xx.x	XX.X-XX.X	XX.X	xx.x-xx.x	XX.X	xx.x-xx.x	XX.X	xx.x-xx.x	
Non-Adjuvanted MCV-5 - Menactra®	xx.x	xx.x-xx.x	XX.X	XX.X-XX.X	xx.x	XX.X-XX.X	XX.X	xx.x-xx.x	xx.x	xx.x-xx.x	

<sup>a Unconditional exact 95% CIs method proposed by Chan and Zhang (1999).

### **TABLE 14.2.1.1(b):**

Secondary Analysis of Percentages of Participants with a ≥4-fold increase in rSBA Titer, by Serogroup - Full Analysis Population

As above

FIGURE 14.2.1.2.1: Reverse Cumulative Distribution Curves of rSBA Titers by Serogroup, Treatment Group and Day - Per-Protocol Population

[figure not shown]

FIGURE 14.2.1.2.2:

Reverse Cumulative Distribution Curves of rSBA Titers by Serogroup, Treatment Group and Day - Full Analysis Population

As above

TABLE 14.2.2.1(a): Secondary Analysis of Percentages of Participants with rSBA Titers ≥8, by serogroup - Per Protocol Population

				M	eningococca	l Polysaccharide				
Treatment Group		A		C		Y		W		X
(Number of Participants)	n (%)	95% CI a	n (%)	95% CI a	n (%)	95% CI a	n (%)	95% CI a	n (%)	95% CI a
Baseline										
Adjuvanted MCV-5 (N=XX)	x (x.x)	xx.x - xx.x	x (x.x)	xx.x - xx.x	x (x.x)	xx.x - xx.x	x (x.x)	xx.x - xx.x	x (x.x)	xx.x - xx.x
Non-adjuvanted MCV-5 (N=XX)	x (x.x)	xx.x - xx.x	x (x.x)	xx.x - xx.x	x (x.x)	xx.x - xx.x	x (x.x)	xx.x - xx.x	x (x.x)	xx.x - xx.x
Menactra® (N=XX)	x (x.x)	xx.x - xx.x	x (x.x)	XX.X - XX.X	x (x.x)	XX.X - XX.X	x (x.x)	XX.X - XX.X	x (x.x)	XX.X - XX.X
Treatment Group Difference	%	95% CI a	0/0	95% CI a	%	95% CI a	%	95% CI a	%	95% CI a
Adjuvanted MCV-5 - Non-Adjuvanted MCV-5	XX.X	xx.x-xx.x	xx.x	XX.X-XX.X	XX.X	XX.X-XX.X	XX.X	XX.X-XX.X	XX.X	xx.x-xx.x
Adjuvanted MCV-5 - Menactra®	XX.X	xx.x-xx.x	XX.X	XX.X-XX.X	XX.X	xx.x-xx.x	xx.x	XX.X-XX.X	XX.X	XX.X-XX.X
Non-Adjuvanted MCV-5 - Menactra®	XX.X	xx.x-xx.x	XX.X	XX.X-XX.X	XX.X	XX.X-XX.X	XX.X	XX.X-XX.X	XX.X	XX.X-XX.X
Day 29										
Adjuvanted MCV-5 (N=XX)	x (x.x)	xx.x - xx.x	x (x.x)	xx.x - xx.x	x (x.x)	xx.x - xx.x	x (x.x)	xx.x - xx.x	x (x.x)	xx.x - xx.x
Non-adjuvanted MCV-5 (N=XX)	x (x.x)	xx.x - xx.x	x (x.x)	xx.x - xx.x	x (x.x)	xx.x - xx.x	x (x.x)	xx.x - xx.x	x (x.x)	xx.x - xx.x
Menactra® (N=XX)	x (x.x)	xx.x - xx.x	x (x.x)	xx.x - xx.x	x (x.x)	xx.x - xx.x	x (x.x)	xx.x - xx.x	x (x.x)	xx.x - xx.x
Treatment Group Difference	%	95% CI a	%	95% CI a	%	95% CI a	%	95% CI a	%	95% CI a
Adjuvanted MCV-5 - Non-Adjuvanted MCV-5	XX.X	xx.x-xx.x	XX.X	XX.X-XX.X	XX.X	xx.x-xx.x	XX.X	xx.x-xx.x	XX.X	xx.x-xx.x
Adjuvanted MCV-5 - Menactra®	XX.X	XX.X-XX.X	XX.X	XX.X-XX.X	XX.X	xx.x-xx.x	xx.x	XX.X-XX.X	xx.x	XX.X-XX.X
Non-Adjuvanted MCV-5 - Menactra®	XX.X	XX.X-XX.X	XX.X	XX.X-XX.X	XX.X	XX.X-XX.X	XX.X	XX.X-XX.X	XX.X	XX.X-XX.X

 $^{\rm a}$  Unconditional exact 95% CIs method proposed by Chan and Zhang (1999).

### **TABLE 14.2.2.1(b):**

Secondary Analysis of Percentages of Participants with rSBA Titers ≥8, by serogroup - Full Analysis Population

### **TABLE 14.2.2.1(c):**

Secondary Analysis of Percentages of Participants with rSBA Titers ≥128, by serogroup – Per-Protocol Population

### **TABLE 14.2.2.1(d):**

Secondary Analysis of Percentages of Participants with rSBA Titers ≥128, by serogroup – Full Analysis Population
As above.

TABLE 14.2.3.1(a): Secondary Analysis of rSBA Geometric Mean Titers per Serogroup - Per Protocol Population

				M	eningococcal	Polysacchari	de			
Treatment Group	1	A	(	С	,	Y	•	W		X
(Number of Participants)	GMT	95% CI	GMT	95% CI	GMT	95% CI	GMT	95% CI	GMT	95% CI
Day 1 (Baseline)										
Adjuvanted MCV-5 (N=XX)										
Non-adjuvanted MCV-5 (N=XX)										
Menactra® (N=XX)										
Treatment Group Comparisons	Ratio	95% CI	Ratio	95% CI	Ratio	95% CI	Ratio	95% CI	Ratio	95% CI
Adjuvanted MCV-5 vs Non-Adjuvanted MCV-5										
Adjuvanted MCV-5 vs Menactra®										
Non-Adjuvanted MCV-5 vs Menactra®										
Day 29										
Adjuvanted MCV-5 (N=XX)										
Non-adjuvanted MCV-5 (N=XX)										
Menactra® (N=XX)										
Treatment Group Comparisons	Ratio	95% CI	Ratio	95% CI	Ratio	95% CI	Ratio	95% CI	Ratio	95% CI
Adjuvanted MCV-5 vs Non-Adjuvanted MCV-5										
Adjuvanted MCV-5 vs Menactra®										
Non-Adjuvanted MCV-5 vs Menactra®										
Fold-Rise From Baseline	GMFR	95% CI	GMFR	95% CI	GMFR	95% CI	GMFR	95% CI	GMFR	95% CI
Adjuvanted MCV-5										
Non-adjuvanted MCV-5										
Menactra ®		_			_	_				_

[figure not shown]
GMT = Geometric Mean Titer; CI = Confidence Interval; GMFR = Geometric Mean Fold Rise; Ratio = Ratio of GMT.

TABLE 14.2.3.1(b): Secondary Analysis of rSBA Geometric Mean Titers per Serogroup - Full Analysis Population

				M	eningococcal	Polysacchari	de			
Treatment Group	1	A	(	С	`	Y	•	W		X
(Number of Participants)	GMT	95% CI	GMT	95% CI	GMT	95% CI	GMT	95% CI	GMT	95% CI
Day 1 (Baseline)										
Adjuvanted MCV-5 (N=XX)										
Non-adjuvanted MCV-5 (N=XX)										
Menactra® (N=XX)										
Treatment Group Comparisons	Ratio	95% CI	Ratio	95% CI	Ratio	95% CI	Ratio	95% CI	Ratio	95% CI
Adjuvanted MCV-5 vs Non-Adjuvanted MCV-5										
Adjuvanted MCV-5 vs Menactra®										
Non-Adjuvanted MCV-5 vs Menactra®										
Day 29										
Adjuvanted MCV-5 (N=XX)										
Non-adjuvanted MCV-5 (N=XX)										
Menactra® (N=XX)										
Treatment Group Comparisons	Ratio	95% CI	Ratio	95% CI	Ratio	95% CI	Ratio	95% CI	Ratio	95% CI
Adjuvanted MCV-5 vs Non-Adjuvanted MCV-5										
Adjuvanted MCV-5 vs Menactra®										
Non-Adjuvanted MCV-5 vs Menactra®										
Fold-Rise From Baseline	GMFR	95% CI	GMFR	95% CI	GMFR	95% CI	GMFR	95% CI	GMFR	95% CI
Adjuvanted MCV-5										
Non-adjuvanted MCV-5										
Menactra ®			_				_		_	

GMT = Geometric Mean Titer; CI = Confidence Interval; GMFR = Geometric Mean Fold Rise; Diff = Difference in GMFR.

FIGURE 14.2.3.2.1: Geometric Mean Titers for rSBA Titer per Serogroup by Treatment Group - Per-Protocol Population

Boxes extend from the 25th to 75th percentiles.

Black horizontal lines indicate the median.

FIGURE 14.2.3.2.2: Geometric Mean Titers for rSBA Titer per Serogroup by Treatment Group - Full Analysis Population

### 14.3 Adverse Events

### **14.3.1 AE** Tables

TABLE 14.3.1.1: Summary of Overall Adverse Events - Safety Population

	MC	vanted CV-5 =X)	MC	uvanted EV-5 =X)	Mena (N=	ectra® =X)
	n	%	n	%	n	%
Solicited Adverse Events						
Any Solicited Adverse Event within 60 minutes post-vaccination	XX	XX.X	XX	XX.X	XX	XX.X
Any Solicited Adverse Event 1-7 days post- vaccination 	XX	XX.X	XX	xx.x	XX	XX.X
Any Local Solicited Event 1-7 days post-vaccination 	XX	XX.X	XX	xx.x	XX	XX.X
Any Systemic Solicited Event 1-7 days post-vaccination 	XX	XX.X	XX	xx.x	XX	XX.X
Any Grade 2 or greater Solicited Local or Systemic Event 1-7 days post-vaccination 	XX	XX.X	XX	XX.X	XX	XX.X
Unsolicited Adverse Events						
Any Serious Adverse Event 	XX	XX.X	XX	XX.X	XX	XX.X
At Least 1 Unsolicited Adverse Event 	XX	XX.X	XX	xx.x	XX	XX.X
Any Grade 2 or greater Unsolicited Adverse Event 	XX	XX.X	XX	xx.x	XX	XX.X
Any Related Unsolicited Adverse Event 	XX	XX.X	XX	xx.x	XX	XX.X
Any Grade 2 or greater Related Unsolicited Adverse Event 	XX	XX.X	XX	XX.X	XX	XX.X

N = Number of participants in the Full Analysis population; n = Number of participants reporting at least one of the specified conditions.

Unsolicited adverse events (AEs) include both serious and non-serious AEs.

A participant is only counted once per row.

<sup>1 Excludes events within 60 minutes of vaccination

<sup>2 Serious adverse events (SAEs) were to be collected for 6 months following vaccination.

<sup>3 Unsolicited AEs were to be reported for 28 days following vaccination.

TABLE 14.3.1.2: Number and Percentage of Participants Experiencing Solicited Events, by Symptom and Treatment Group - Full Analysis Population

		ed MCV-5 =X)		anted MCV-5		actra® =X)	MCV-5 + Adj versus	MCV-5 versus
Symptom	n (%)	(95% CI)	n (%)	(95% CI)	n (%)	(95% CI)	Menactra p-value 	Menactra p-value 
Local Reactions								
Pain at injection site								
Erythema at injection site								
Swelling at injection site								
Any Local Symptom								
Systemic Symptoms								
Fever								
Headache								
Fatigue/malaise								
Joint pain/arthralgia								
Muscle pain/myalgia								
Diarrhea								
Anorexia								
Chills								
Vomiting								
Any Systemic Symptom								
Any Systemic or Local Symptom								

N = number of participants in the Full Analysis population.

<sup>1 Fisher's exact 2-tailed test of the proportion of participants with an event.

TABLE 14.3.1.3: Number and Percentage of Participants Experiencing Solicited Events by Symptom, Maximum Severity and Treatment Group - Safety Population

		MO	vanted CV-5 =X)	MO	juvanted CV-5 =X)	Menactra® (N=X)	
Symptom	Severity	n	%	n	%	n	%
Any Symptom	None						
	Mild						
	Moderate						
	Severe						
	Life-Threatening						
Any Local Symptom	None						
	Mild						
	Moderate						
	Severe						
	Life-Threatening						
Pain at Injection Site	None						
	Mild						
	Moderate						
	Severe						
	Life-Threatening						
Erythema at Injection Site	None						
	Mild						
	Moderate						
	Severe						
Swelling at injection site	None						
	Mild						
	Moderate						
	Severe						
	Life-Threatening						

N = Number of participants in the Full Analysis population; Severity is based off of the maximum severity reported post vaccination.

TABLE 14.3.1.3: Number and Percentage of Participants Experiencing Solicited Events by Symptom, Maximum Severity and Treatment Group - Safety Population

		M	vanted CV-5 (=X)	MO	juvanted CV-5 (=X)		actra® =X)
Symptom	Severity	n	%	n	%	n	%
Any Systemic Symptom	None						
	Mild						
	Moderate						
	Severe						
	Life-Threatening						
Elevated Oral Temperature	None						
	Mild						
	Moderate						
	Severe						
	Life-Threatening						
Headache	None						
	Mild						
	Moderate						
	Severe						
	Life-Threatening						
Fatigue/malaise	None						
	Mild						
	Moderate						
	Severe						
	Life-Threatening						
Joint pain/arthralgia	None						
	Mild						
	Moderate						
	Severe						
	Life-Threatening						
Muscle pain/myalgia	None						
	Mild						
	Moderate						
	Severe						
	Life-Threatening						
Diarrhea	None						
	Mild						
	Moderate						
	Severe						
	Life-Threatening						
Anorexia	None						
	Mild						
	Moderate						

TABLE 14.3.1.3: Number and Percentage of Participants Experiencing Solicited Events by Symptom, Maximum Severity and Treatment Group - Safety Population

		MO	vanted CV-5 =X)	MC	juvanted CV-5 =X)	Menactra® (N=X)	
Symptom	Severity	n	%	n	%	n	%
	Severe						
	Life-Threatening						
Chills	None						
	Mild						
	Moderate						
	Severe						
	Life-Threatening						
Vomiting	None						
	Mild						
	Moderate						
	Severe						
	Life-Threatening						

N = Number of participants in the Full Analysis population; Severity is based off of the maximum severity reported post vaccination.

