#### **Endpoints:**

Summaries by product received including the number and percentage of participants experiencing:

- immediate AEs within 60 minutes post-vaccination;
- solicited local or systemic post vaccination reactogenicity reactions within seven days following vaccination (Days one through seven);
- any SAE within six months following vaccination;
- any AE within 28 days following vaccination;
- any Grade 2 or greater solicited local or systemic post vaccination reactions within seven days following vaccination;
- any Grade 2 or greater unsolicited AE within 28 days following vaccination;
- any unsolicited AE within 28 days following vaccination judged to be related to study product; and
- any Grade 2 or greater unsolicited AE within 28 days following vaccination judged to be related to study product.

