#### **Analysis of Primary Safety Objective**

The primary aim of the study is to assess the safety of the study vaccine. All safety data (solicited local and systemic reactions and unsolicited AEs and SAEs) collected after participants are exposed to the study product will be included in the primary analysis of safety.

To assess safety, the number and percentage of participants experiencing at least one AE, and the number and percentage of participants experiencing each specific AE, categorized by body system and preferred term, will be tabulated by product received along with their corresponding two-sided exact 95% confidence intervals.

Fisher's exact test will be used to compare the proportion of participants with solicited local and systemic reactogenicity events between the MCV-5 group and the Menactra® Group. The primary purpose of statistical comparisons is to screen out potential solicited reactogenicity events that need further clinical evaluation. Therefore, they are not considered formal statistical hypothesis tests and it is acknowledged that there will be inflated Type I errors (i.e. inflated false statistical significances) from performing multiple unadjusted comparisons.

Changes in clinical laboratory values from baseline to end of treatment/follow-up will be analyzed descriptively.

To facilitate the planning of the follow-up trial, analysis of unblinded primary safety data up to Visit 4 (Day 29) by treatment groups will be made available to the Sponsor after all participants have completed this visit and their data have been cleaned and verified.

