#### 9.4.1 Primary Summary of Adverse Events

The primary safety objective is to evaluate the safety of adjuvanted and non-adjuvanted formulations of MCV-5 vaccine in healthy adults. To accomplish this objective, an overall summary of adverse events will be presented in Table 14.3.1.1. The table will summarize the number and percentage of participants in each treatment group experiencing the following:

- immediate solicited AEs within 60 minutes post-vaccination;
- solicited local or systemic post vaccination reactogenicity reactions within seven days following vaccination (Days one through seven);
- any SAE;
- any unsolicited AE;
- any Grade 2 or greater solicited local or systemic post vaccination reactions within seven days following vaccination;
- any Grade 2 or greater unsolicited AE;
- any unsolicited AE judged to be related to study product; and
- any Grade 2 or greater unsolicited AE following vaccination judged to be related to study product.

Note: summaries of unsolicited AEs will include SAEs.

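### Footnote 1 of SAP Table 14.3.1.1 removes first-hour reactions from four seven-day solicited rows that the protocol and SAP text define without that exclusion

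*SAP*

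**What the plan says.** **The table's role.** SAP 9.4.1 restates the primary safety objective and continues: "To accomplish this objective, an overall summary of adverse events will be presented in Table 14.3.1.1".

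**The definition.** Protocol 7.3.1 lists, as a primary safety summary, "solicited local or systemic post vaccination reactogenicity reactions within seven days following vaccination (Days one through seven"). It also lists "any Grade 2 or greater solicited local or systemic post vaccination reactions within seven days following vaccination". SAP 9.4.1 repeats both items. Neither document removes the first hour. The protocol synopsis and SAP 3.3 both make the day of vaccination Day 1.

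**The shell.** In SAP 14.3.1, Table 14.3.1.1 has five solicited rows. The first counts any solicited event within 60 minutes. The other four cover days 1 to 7 and carry footnote 1: "Excludes events within 60 minutes of vaccination".

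**Scope of the analysis.** Protocol 7.5.2 states that all safety data "collected after participants are exposed to the study product will be included in the primary analysis of safety".

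**Immediate events.** Protocol 7.3.1 lists "immediate AEs within 60 minutes post-vaccination". SAP 9.4.1 has "immediate solicited AEs within 60 minutes post-vaccination", and the shell follows the SAP.

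**The concern.** The printed footnote and the written definition give different counts for the same row. A programmer following the shell would leave out a participant whose only reaction was seen at the 60-minute check. One following SAP 9.4.1 would count that participant. SAP section 12, the place for changes in planned analyses, records no reason for the difference.

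At stake are the headline seven-day and Grade 2+ reactogenicity proportions in a first-in-human trial with 20 participants per arm. The same arm could also show one number of participants with any solicited reaction in Table 14.3.1.1 and a higher one in Table 14.3.1.3.

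The immediate-AE wording raises a smaller, separate question. The protocol's item is not limited to solicited terms, and the synopsis describes the 60-minute observation as looking for other AEs as well.

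**Working it through.** **1. Is the first hour inside the defined window?** Day 1 is the vaccination day (protocol synopsis, SAP 3.3). The window is Days 1 to 7 (protocol 7.3.1, SAP 9.4.1). Solicited reactions are assessed at 60 minutes (protocol 5.2.4, SAP 9.4.2). So a reaction recorded at 60 minutes is a Day 1 solicited reaction under both definitions.

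**2. Can the defined proportion be rebuilt from Table 14.3.1.1?** Let *a* be the number of participants in the 60-minute row and *b* the number in the footnoted any-solicited row. The defined count is the number with either, which lies between max(*a*, *b*) and min(20, *a* + *b*). The overlap is not shown, so the count is fixed only when these limits coincide. When *b* is at least *a* and *a* + *b* is at most 20, the uncertainty is *a*/20: 5, 10 or 15 points for *a* = 1, 2 or 3. For the local, systemic and Grade 2+ rows less is known, because the 60-minute row has no grade and no local/systemic split.

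**3. Comparison with the other solicited tables.**

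| SAP table | Treatment of first-hour events |
|---|---|
| 14.3.1.1, four seven-day rows | Excluded by footnote 1 |
| 14.3.1.2 (rates, CIs, Fisher p-values) | No exclusion stated; window not spelled out |
| 14.3.1.3 (maximum severity) | Footnote takes the maximum reported after vaccination, which reads as including them |
| 14.3.1.4 (by day and severity) | Own 60-minute column, by severity and symptom |

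**4. The plan's own precision figures** (protocol 7.4, n = 20):

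- Chance of at least one event at an 11% rate: 1 − 0.89^20 = 0.903, matching the stated value of more than 90%.
- One-sided 95% upper bound for 0/20: 1 − 0.05^(1/20) = 13.9%, matching the stated 14% or so.

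**5. Size.** Each participant whose only qualifying reaction is at the 60-minute check lowers a row by 1/20 = 5 points. Zero to three such participants give 0, 5, 10 or 15 points. Where no other participant in the arm has a qualifying event (exact bounds):

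| First-hour-only participants | Row with footnote: one-sided 95% upper bound | Row as defined: one-sided 95% upper bound |
|---|---|---|
| 1 | 0/20: 13.9% | 1/20: 21.6% |
| 2 | 0/20: 13.9% | 2/20: 28.3% |

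The documents give no rate *q* of first-hour-only reactors. With 1 − (1 − *q*)^20, assumed values of *q* = 1%, 2%, 5% and 10% give an 18%, 33%, 64% and 88% chance that an arm has at least one.

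**6. Immediate AEs.** The SAP row omits unsolicited events in the first hour. Yet for missing data, SAP 6.5 groups immediate AEs with unsolicited AEs and SAEs and gives solicited events separate rules. Listing 16.2.7.2 carries a start date and days after dosing but no time, so it cannot mark an event as immediate.

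**The case against.** The best defence is that the footnote makes a partition. SAP 9.4.2 describes a 60-minute collection followed by daily collection, Table 14.3.1.4 gives 60 minutes and Day 1 separate columns, and the daily records come from the memory aid. Both documents list the immediate item separately from the seven-day item. On this view the footnote only keeps two sources apart.

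The intent is plausible, but the result still conflicts with the definition. Listing immediate events separately does not remove them from a window that starts on the vaccination day, and the ungraded row cannot supply what the four rows omit.

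Other parts of the defence stand. Protocol 7.5.2 requires post-exposure data to be in the primary safety analysis; it does not require every event in every row, so the case rests on the window definition. The safety analysis is descriptive, and no decision threshold is attached to these rows. A reaction still present later on Day 1 can be recorded again in the memory aid. The footnote does not say how to treat a reaction that starts in the first hour and continues, so only reactions confined to that hour clearly drop out.

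On immediate AEs, protocol 5.2.4 lists only solicited items for recording at 60 minutes, which partly explains the SAP wording.

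**Conclusion.** The conflict is real and confined to one overview table, which is the one named for the primary objective. Its four seven-day solicited rows can be lower than defined by 5 points per affected participant, and by nothing if no one reacts only in the first hour. This rests on 20 participants per arm and on reading the footnote as removing at least the reactions confined to that hour.

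Three stronger readings are tempting but unsupported:

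- **First-hour data, or Grade 2+ reactions in that hour, disappear from the report.** They do not. Table 14.3.1.4 shows them by symptom and severity, and Table 14.3.1.3 reads as including them.
- **Unsolicited events in the first hour, such as an allergic reaction, go unreported.** They still count in the 28-day unsolicited rows and appear in the listing. What is missing is their identification as immediate. This part is a minor departure from protocol 7.3.1.
- **Showing "any AE within 28 days following vaccination" as unsolicited only is a further error.** The primary endpoint wording in protocol 2.4.4 and SAP 3.2.1 names unsolicited AEs for that period, so the SAP's choice is defensible.

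**What to change.** 1. Delete footnote 1 from Table 14.3.1.1, so that the four rows count every solicited reaction from vaccination through Day 7. Keep the 60-minute row and label it a subset.
2. State the same window in Table 14.3.1.2, and confirm it in Table 14.3.1.3, so that the three tables agree.
3. Check the interim shells in SAP Appendix I for the same footnote, and settle the matter before the unblinded Day 29 safety analysis is run.
4. For immediate AEs, check whether the CRF identifies unsolicited events seen in the first hour. If it does, restore the item in SAP 9.4.1 and the shell to any AE within 60 minutes. If it does not, keep the row as solicited only and record the narrowing in SAP section 12 as a change from protocol 7.3.1.

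Items 1 to 3 cost SAP wording and shell edits; reported seven-day rates may be slightly higher. Item 4 also needs a look at the CRF, which is not among the documents. No sample size or precision figure changes.

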**TABLE 14.3.1.4:** 

Number and Percentage of Participants Experiencing Solicited Events by Severity, at 60 minutes and at Day 1 through Day 8 Post Vaccination by Treatment Group - Full Analysis Population

TABLE 14.3.1.4(a) Any Local or Systemic Symptom

	60 mins (N=X)	Day 1 (N=X)	Day 2 (N=X)	Day 3 (N=X)	Day 4 (N=X)	Day 5 (N=X)	Day 6 (N=X)	Day 7 (N=X)	Day 8 (N=X)
Adjuvanted MCV-5									
N									
None – n (%)									
Mild – n (%)									
Moderate – n (%)									
Severe – n (%)									
Life-Threatening – n (%)									
Not Reported – n (%)									
MCV-5									
N									
None – n (%)									
Mild-n (%)									
Moderate – n (%)									
Severe – n (%)									
Life-Threatening – n (%)									
Not Reported – n (%)									
Menactra®									
N									
None – n (%)									
Mild – n (%)									
Moderate – n (%)									
Severe – n (%)									
Life-Threatening – n (%)									
Not Reported – n (%)									

N = Number of participants in the Full Analysis Population. Severity is the maximum severity reported for each participant for each day.

